11.3.5 Pregnancy Tests

All females who are pre-menses and FOCBP will undergo serum pregnancy testing at the Baseline and Week 12 study visits, and urine pregnancy testing at Screening, prior to randomization at Baseline, and at Weeks 2, 4, 8 and 12. The urine pregnancy tests will be supplied by the CRO/designee.

11.4 Adverse Events

11.4.1 Definition of Adverse Event

An AE is any untoward medical occurrence in a patient or clinical investigation subject administered a medicinal product and which does not necessarily have a causal relationship with the study drug. AEs include any unfavorable and unintended illness, sign, symptom, clinically significant laboratory test abnormality, or disease temporally associated with the use of a medicinal product that has appeared or worsened during the course of the clinical trial, regardless of causal relationship to the study drug(s) under study. The collection of AEs will begin following the subject's completion of the consent process to participate in the study.

11.4.2 Documenting Adverse Experiences

It is the responsibility of the investigator to document all AEs that occur during the course of the study. The AEs should be documented as a single medical diagnosis. When this is not possible, the AE should be documented in terms of signs and/or symptoms observed by the investigator or reported by the subject at each study visit. Each AE which appears to be independent of any prior event will be reported separately.

All AEs occurring after the subject signs the informed consent through the last study visit must be reported, regardless of whether or not the AEs are considered study drug-related. All AEs, whether in response to a query, observed by the study center personnel, or reported spontaneously by the subject, will be recorded. Any AEs deemed related to treatment reported or observed at the final study/treatment visit will be followed until stabilization or resolution.

At each visit during the study, the subject will be assessed for the occurrence of new and ongoing AEs. Cutaneous safety and tolerability signs and symptoms that result in the subject's requiring a concomitant therapy, interruption of treatment, or discontinuation from the study will be reported as an AE. The following data will be collected on all AEs and recorded on the appropriate eCRF:

- Event description (diagnosis preferred, if unknown, record the signs/symptoms)
- Onset date and end date
- Maximum intensity (severity)
- Seriousness
- Action taken regarding study drug
- Corrective treatment, if given
- Outcome

In addition, the investigator's assessment of causality will be recorded.

Vital sign and laboratory abnormalities are to be recorded as AEs only if they are clinically significant (for example: are symptomatic, requiring corrective treatment, increased monitoring, leading to discontinuation or fulfilling a seriousness criterion).

11.4.3 Serious Adverse Events

All AEs will be assessed as either serious or nonserious. An SAE is defined as any untoward medical occurrence that, at any dose:

- Results in death.
- Is immediately life threatening, (the term "life threatening" in the definition of "serious" refers to an event in which the subject is at risk of death at the time of the event; it does not refer to an event which hypothetically might have caused death if it were more severe).
- Requires in patient hospitalization or prolongation of existing hospitalization (hospitalization for elective surgery for a baseline condition is not considered an AE).
- Results in persistent or significant disability/incapacity (permanent or substantial disruption of a person's ability to conduct normal life functions).
- Is a congenital anomaly/birth defect.
- Is a medically important event that may not be immediately life threatening or result in death or hospitalization, but may jeopardize the subject and may require medical or surgical intervention to prevent one of the above listed outcomes; examples of such events include, but are not limited to, allergic bronchospasm requiring intensive treatment in an emergency room or at home; blood dyscrasias or convulsions that do not result in inpatient hospitalization.

Note: A spontaneous abortion will be considered an SAE, and must be reported to the Sponsor within 24 hours of your awareness of the event as outlined under Section 11.4.6.

11.4.4 Assessment of Severity

The severity assigned to an AE should be determined by the maximum severity of the AE. The categories described below should be used to estimate the severity of AEs:

- Mild: Transient or mild discomfort which is easily tolerated; no limitation in activity; no medical intervention/therapy required.
- Moderate: Mild to moderate limitation in activity, but does not prevent usual activity; some assistance may be needed; no or minimal medical intervention/therapy required.
- Severe: Marked limitation in activity; some assistance usually required; medical intervention/therapy required; hospitalization or prolongation of current hospitalization possible; may be incapacitating or life threatening.

11.4.5 Assessment of Causality

The investigator should assess the relationship of the AE, if any, to the study drug as either "Related" or "Not Related." The following should be taken into account when assessing AE/SAE causality:

- Related: There is at least a reasonable possibility that the AE/SAE is related to the study drug. Reasonable possibility means that there is evidence to suggest a causal relationship between the drug and the AE.
- Not Related: There is little or no reasonable possibility that the AE/SAE is related to
 the study drug. This assessment implies that the AE/SAE has little or no temporal
 relationship to the study drug and/or a more likely or certain alternative etiology
 exists.

The following should be considered when assessing AE/SAE causality:

- Positive temporal relationship to study drug, such as if the study drug was withdrawn and the SAE resolved, or the event recurred after re-introduction
- If there is a reasonable possibility that the AE is associated with an underlying or concomitant illness
- Possible association with previous or concomitant therapy
- No temporal relationship to the study drug and/or a more likely alternative etiology exists.
- If the AE is directly related to study procedures or there is a lack of efficacy

11.4.6 Reporting of Serious Adverse Events

Adverse events classified as "serious" require expeditious handling and reporting to sponsor or designee within 24 hours of study center notification to comply with regulatory requirements.

All SAEs, whether related or unrelated to study drug, must be immediately reported to the medical monitor and CRO contact within 24 hours of the investigator's awareness of the event. All SAEs must be reported via secure transmission and must be submitted on a written SAE report form signed by the investigator within 24 hours of the investigator's awareness of the event. Contact details for SAE submission and method of secure submission are provided within the SAE form.

Investigators should not wait to receive additional information to fully document the event before notifying medical monitor and Sponsor of an SAE. If only limited information is initially available, follow-up reports are required. Additional relevant information such as hospital records and autopsy reports should be provided to the Sponsor as soon as they are available. Should the investigator become aware of an SAE (regardless of its relationship to study drug) that occurs within 30 days after stopping the study drug, the SAE must be reported in accordance with procedures specified in this protocol.

All deaths of subjects, regardless of cause, and which are known to the Investigator will be reported on the appropriate eCRF for up to 30 days after the administration of study drug, regardless of the Investigator's opinion regarding drug relationship. Documentation of the subject's cause of death and a copy of the pseudonymized autopsy or pseudonymized hospital report will also be provided. The Medical Monitor and CRO contact must be notified within 24 hours of knowledge of the event by telephone and submission of an SAE form for all subject deaths. Written follow-up must be received by the IRB/IEC and competent authority within five (5) calendar days of initial notification as required by local regulations. If cause of death is not available within 24-hour reporting period, "death" must be reported as SAE term to meet timelines and the cause of death actively queried and submitted as a follow-up as soon as available

The investigator should take all appropriate measures to ensure the safety of the subjects, notably he/she should follow a subject with an SAE until the event has resolved or the condition has stabilized. This may imply that follow-up will continue after the subject has left the study, and that additional investigations may be requested by the Sponsor. When a SAE persists at the end of the study, the investigator will conduct follow-up contacts with the subject until the investigator/Sponsor agree the event is satisfactorily resolved and/or stabilized. If at any time after 30 days after administration of study drug, the investigator becomes aware of an SAE which he/she feels is related to study drug or procedure, this must also be reported immediately (within 24 hours of knowledge of occurrence) by telephone and secure transmission to the medical monitor and Sponsor and/or Sponsor designee.

11.4.7 Expedited Serious Adverse Event Reports

Expedited SAE reports are those that are both unexpected based on the reference document (Investigator Brochure) and are related (i.e., the relationship cannot be ruled out) to the study drug. The Sponsor will notify regulatory authorities of these AEs and all participating study centers in writing for submission by the investigator to the IRB/IEC as required by local regulations.

Upon receiving such notices, the investigator must review and retain the notice with the Investigator Brochure and immediately submit a copy of this information to the responsible IRB/IEC according to local regulations. The investigator should also comply with the IRB/IEC procedures for reporting any other safety information.

11.4.8 Pregnancy

All pre-menses females and FOCBP must use an effective method of birth control during the course of the study, in a manner such that risk of contraceptive failure is minimized. Abstinence is allowed as a birth control method.

Before enrolling a pre-menses female or FOCBP in this clinical study, the investigator must review the following information about study participation:

- Informed consent requirements
- Contraceptives in current use

Following review of this information and appropriate subject counseling, the investigator or designee and the subject must sign the informed consent/assent before study enrollment.

During the study, all pre-menses females and FOCBP should be instructed to contact the investigator immediately if they suspect they might be pregnant (eg, missed or late menstrual period).

If a subject or investigator suspects that the subject may be pregnant prior to study enrollment, the study drug must be withheld until the results of laboratory pregnancy testing are available. If pregnancy is confirmed, the subject must not receive study drug and must not be enrolled in the study. If pregnancy is suspected while the subject is receiving study drug, the study drug must immediately be withheld until the result of pregnancy testing is known. If pregnancy is confirmed, the study drug will be permanently discontinued and the subject will be followed until the pregnancy comes to term. A Pregnancy Report Form will be submitted to the sponsor, initially and at the end of the pregnancy, which includes the outcome of the pregnancy and any complications occurring during the pregnancy or the delivery. If any SAEs are associated with the pregnancy, including spontaneous abortion/miscarriage, an SAE form must be filled out in addition to the Pregnancy Report Form and submitted as per section 11.4.6.

All confirmed pregnancies must be immediately reported to the medical monitor and CRO contact within 24 hours of the investigator's awareness of the pregnancy. All confirmed

pregnancies are to be reported on a pregnancy form using the same reporting procedure for an SAE under Section 11.4.6.

12 Statistics

All statistical processing will be performed using SAS® version 9.4 or later unless otherwise stated. Statistical significance for superiority analyses will be based on two-tailed tests of the null hypothesis resulting in p-values of 0.05 or less. Non-inferiority of IDP-126 Gel to Epiduo® Forte will be assessed with 95% confidence intervals.

The primary method of handling missing efficacy data will be based on estimation using the method of Markov Chain Monte Carlo (MCMC) imputation. Estimation will be done for each treatment group separately so that the pattern of missingness for one group does not influence the estimation of missing data for another group. Groups of complete datasets following the estimation will be concatenated to form analysis datasets for the analyses and subsequent imputation result inference with SAS PROC MIANALYZE. Descriptive statistics will also be derived from the multiply imputed datasets.

A statistical analysis plan, describing all statistical analyses will be provided as a separate document. The SAP will be finalized prior to unblinding of the study treatments.

Evaluations and Analyses

Inflammatory lesions and non-inflammatory lesions will be recorded for each subject at Baseline and at Weeks 2, 4, 8, and 12. The absolute and percent change from baseline of inflammatory lesions and non-inflammatory lesions will be derived for each subject at Weeks 2, 4, 8, and 12. The EGSS will be recorded for each Subject. The EGSS will be dichotomized into "success" and

"failure" at Week 2, 4, 8 and 12 with a subject considered a success for those visits if the EGSS is at least 2 grades less than baseline and are Clear or Almost Clear. The TSS will be recorded for applicable subjects with truncal acne, and will be summarized at Week 2, 4, 8, and 12, with the percentage of subjects achieving at least a 2-grade reduction from baseline included in the summary. The TSS will be dichotomized into "success" and "failure" at Week 2, 4, 8 and 12

with a subject considered a success for those visits if the TSS is at least 2 grades less than baseline.

Subjects will be asked to complete the Acne-Specific Quality of Life Questionnaire at Baseline

The two IDP-126 Vehicle Gel groups are combined for purposes of analyses.

12.1 Assessment of Efficacy

and Week 12.

Primary, secondary and supportive efficacy analyses will be conducted on the ITT (primary) population. Primary efficacy analyses will be conducted on the PP (supportive) population.

12.1.1 Primary Efficacy

There are three co-primary efficacy endpoints:

- Absolute change from Baseline to Week 12 in inflammatory lesion counts
- Absolute change from Baseline to Week 12 in non-inflammatory lesion counts
- Percentage of subjects who achieve at least a two-grade reduction from Baseline and are "Clear" or "Almost Clear" at Week 12 in the EGSS.

12.1.2 Secondary Efficacy

The secondary efficacy endpoints will be the following:

- Absolute change in inflammatory and non-inflammatory lesion counts from Baseline at Weeks 2, 4, and 8
- Percent of subjects who achieve at least a 2-grade reduction from Baseline and are "Clear" or "Almost Clear" at Week 2, 4, and 8 in the EGSS
- Percent change in inflammatory and non-inflammatory lesion counts from Baseline at Weeks 2, 4, 8, and 12
- Percent of subjects who achieve at least a 2-grade reduction from Baseline at Week 2, 4, 8 and 12 in the TSS.

12.1.3 Non-Inferiority for Lesion Count Variables Evaluator's Global Severity Score

This section provides the basic model and statistical approach which is used in combination with the multiple imputation procedures described in Section 12.1.9. Non-inferiority of IDP-126 Gel to Epiduo[®] Forte will be assessed with 95% confidence intervals with the following non-inferiority margins:

- Absolute change from Baseline to Week 12 in inflammatory lesion counts: 2.1
- Absolute change from Baseline to Week 12 in non-inflammatory lesion counts: 2.1
- Percentage of subjects who achieve at least a two-grade reduction from baseline and are "Clear" or "Almost Clear" at Week 12 in the Evaluator's Global Severity Score: 10%

Confidence intervals of the difference in means (IDP-126 – Epiduo[®] Forte) for the absolute change from Baseline in inflammatory and non-inflammatory lesions will be based on based on an ANCOVA with factors of treatment and analysis center and the respective Baseline lesion count as a covariate If the treatment-by-analysis center interaction effect is significant at an alpha less than 0.10, then the effect will be included in the model; otherwise it will be removed.

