- 3) Percentage of subjects who achieve at least a two-grade reduction from baseline and are "Clear" or "Almost Clear" at Week 12 in the Evaluator's Global Severity Score: 10%

Confidence intervals and superiority testing of lesion counts will be based on an ANCOVA with factors of treatment and analysis center and the respective Baseline lesion count as a covariate.

Confidence intervals and superiority testing of the dichotomized EGSS will be based on logistic regression with factors of treatment group and analysis center. The TSS will be recorded for applicable subjects with truncal acne, and will be summarized at Week 2, 4, 8, and 12, with the percentage of subjects achieving at least a 2-grade reduction from baseline included in the summary.

The primary method of handling missing efficacy data will be based on estimation using the method of Markov Chain Monte Carlo (MCMC) imputation. Other methods, as well as the MCMC imputation, will be specified in the statistical analysis plan which will be finalized prior to data base lock.

Populations Analyzed and Treatment Groups:

Inflammatory and non-inflammatory lesion counts will be recorded for each Subject at Baseline and at Weeks 2, 4, 8, and 12. The absolute and percent change from Baseline in inflammatory and non-inflammatory lesions will be derived for each Subject at Weeks 2, 4, 8, and 12.

The EGSS will be recorded for each Subject. The EGSS will be dichotomized into "success" and "failure" with a subject considered a success if the Evaluator's Global Severity Score at Week 2, 4, 8, and 12 is at least 2 grades less than baseline and Clear or Almost Clear.

Populations Analyzed:

An intent-to-treat (ITT) analysis will be conducted on all study subjects. The ITT population will consist of all randomized subjects who received study drug.

All subjects who are randomized and receive at least 1 confirmed dose of study drug will be included in the Safety population.

A per-protocol (PP) analysis will also be conducted. Subjects will be eligible for the PP analysis if they complete the 12-week evaluation without noteworthy study protocol violations (i.e., any subject or investigator activity that could have possibly interfered with the therapeutic administration of the treatment or the precise evaluation of treatment efficacy). The PP population will include subjects in the ITT population who do not meet any of the following criteria:

- Failed any of the inclusion/exclusion criteria.

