- Have taken any interfering concomitant medications.
- Did not attend the Week 12 visit, with the exception of a discontinuation from the study due to an AE related to study treatment or documented lack of treatment effect.
- Missed more than 1 post baseline study visit prior to Week 12.
- Have not been compliant with the dosing regimen (i.e., subjects may not miss more than 5 consecutive days of dosing and must take 80%-120% of expected doses). The number of expected doses will be determined for each subject based on the length of their participation in the study.
- Out of visit window at the Week 12 visit.

Subjects who discontinue from the study due to an adverse event related to study treatment or documented lack of treatment effect (and/or worsening of condition) will be included in the PP population. Prior to breaking the blind, other additional criteria may be added to the list to accommodate for unforeseen events that occurred during the conduct of the trial that result in noteworthy study protocol violations.

Approximately 660 subjects will be randomized in a 2:2:1:1 ratio to the following treatment groups:

- 220 Subjects to IDP-126 Gel (clindamycin phosphate 1.2%/BPO 3.1%/adapalene 0.15%)
- 220 Subjects to Epiduo[®] Forte Gel (adapalene 0.3%/BPO 2.5%)

- 110 Subjects to IDP-126 Vehicle Gel (stored at 2-8°C)
- 110 Subjects to IDP-126 Vehicle Gel (stored at controlled room temperature)

Subject demographic and baseline characteristics will be summarized by treatment group using descriptive statistics for the ITT, PP, and Safety analysis sets.

Efficacy Evaluation:

Primary efficacy analyses will be conducted on the ITT (primary) and PP (supportive) populations. Secondary analyses will be conducted on the ITT population.

Primary:

Co-primary efficacy analyses include the absolute change from baseline in inflammatory and in non-inflammatory lesions, and the dichotomized Evaluator's Global Severity Score. The pre-specified time point will be Week 12. All of the testing relating to the analysis of inflammatory and non-inflammatory lesions will use the methods introduced in Section 12.

Secondary:

Secondary efficacy endpoints include absolute and percent change in inflammatory and non-inflammatory lesion counts from baseline to Weeks 2, 4, 8, and 12 and also percentage of subjects with at least a two-grade improvement and are "clear" to "almost clear" in the Evaluator's Global Severity Score from baseline at each visit.

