12.1.7 Missing Efficacy Data Imputations

Lesion Count Variable Missing Data Imputation

Missing data will be estimated by multiple imputation and subsequently analyzed. Missing lesion count data will be derived for the analysis using the method of Markov Chain Monte Carlo (MCMC) multiple imputation. The pattern of missing observations in each treatment group will not influence the missing value estimation in the other because the imputation is being conducted independently for each treatment group.

Multiple imputation and subsequent analysis will involve 4 distinct phases with these principal tasks:

1. Create a data set of subjects, one for each treatment group, with observed values and those needing estimation by MCMC. The missing lesion count values in each data set will be filled in using the MCMC method 5 times to generate 5 data sets. The resulting data sets for each treatment arm will be combined into one complete data set for each imputation.

Syntax:

```
proc mi data=datain out=dataout seed=&seed. nimpute=5 <options>;
  where trtpn=(1, 2, 3);
  mcmc chain=multiple;
  var baseline week2 week4 week8 week12;
run;
```

- 3. For each complete data set, the absolute change in lesion counts will be computed. Each complete data set will be analyzed as specified for the particular analysis.
- 4. The results from these analyses will be combined into a single inference using SAS PROC MIANALYZE.

A total of 6 random seeds will be needed to impute inflammatory lesion counts and non-inflammatory lesion counts for the five treatment groups. Those 6 random seeds have been prespecified by using a random number generator:

- Inflammatory Lesion Counts; IDP-126 Gel: Seed=1228911621
- Inflammatory Lesion Counts; Epiduo® Forte Gel: Seed=1083128177
- Inflammatory Lesion Counts; IDP-126 Vehicle Gel: Seed=138767001
- Non-Inflammatory Lesion Counts; IDP-126 Gel: Seed=239363547
- Non-Inflammatory Lesion Counts; Epiduo® Forte Gel: Seed=1663970906
- Non-Inflammatory Lesion Counts; IDP-126 Vehicle Gel: Seed=1896067066

EGSS Missing Data Imputation

A similar procedure will be used for the analyses based on proportion of EGSS successes wherein the ANCOVA analysis is replaced with a logistic regression analysis. Specifically, missing EGSS values from which the dichotomized EGSS is derived will be estimated by MCMC. The pattern of missing observations in each treatment group will not influence the

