The consistency of treatment response will be investigated across the analysis centers subsequent to combining the data as described above. Statistical tests will be conducted to identify if there

are extreme analysis centers that could affect the interpretation of common statistical and clinical conclusions. An analysis center by treatment interaction will be included in the primary variable analyses to test for parallel treatment effect at an alpha level of 0.10. Change from baseline in inflammatory lesions and non-inflammatory lesions will be analyzed with an ANCOVA with factors of treatment, analysis center, and treatment by analysis center interaction and the respective baseline lesion count variable as a covariate. For the purpose of testing consistency of treatment response, the dichotomized EGSS will be analyzed with a logistic regression procedure with factors of treatment, analysis center, and treatment by analysis center interaction. Further examination will follow for any variables that have a significant ANCOVA or logistic regression interaction term. In the event that the ANCOVA or logistic regression interaction (referred to henceforth as the "appropriate test") p-value is less than or equal to 0.10, a sensitivity analysis that excludes analysis centers with the extreme efficacy result will be performed to determine the robustness of the treatment effect. On the other hand, if the outcome of the appropriate test has a p-value greater than 0.10, then the conclusions from the pooled data will be considered to be free of the impact of extreme analysis centers.

The first step in conducting a sensitivity analysis is to identify the extreme analysis center or centers that contribute to the statistical significance of the appropriate test. The process involves submitting subsets of analysis centers to the appropriate test and observing the appropriate test p-value for the subset. Subsets with p-values greater than 0.10 for the appropriate test are considered homogeneous.

The search for an extreme analysis center begins by analyzing all subsets that can be created by excluding one analysis center. If one or more of the subsets result in an appropriate test p-value greater than or equal to 0.10, then the analysis center excluded from the subset with the largest p-value for the appropriate test is deemed to be the extreme analysis center.

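### Section 12.8.4 treats a non-significant treatment-by-center test (p > 0.10) as proof that no center distorts the pooled result, which the test cannot show; its use to choose the lesion-count model is a smaller flaw

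*Combined protocol and SAP*

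**What the plan says.** **Consistency rule (12.8.4).** "An analysis center by treatment interaction will be included in the primary variable analyses to test for parallel treatment effect", at a level of 0.10. For EGSS, "the dichotomized EGSS will be analyzed with a logistic regression procedure with factors of treatment, analysis center, and treatment by analysis center interaction". If the p-value is at or below 0.10, "a sensitivity analysis that excludes analysis centers with the extreme efficacy result will be performed". If it is above 0.10, "then the conclusions from the pooled data will be considered to be free of the impact of extreme analysis centers". The section cautions about the exclusion search, which removes subjects non-randomly and is post hoc. It does not qualify the statement made when p exceeds 0.10.

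**Primary lesion-count model.** 12.1.3 (non-inferiority) and 12.1.4 (superiority) carry the same rule: "If the treatment-by-analysis center interaction effect is significant at an alpha less than 0.10, then the effect will be included in the model"; otherwise the term is dropped. The synopsis (Statistical Methods) has no such step: "superiority testing of lesion counts will be based on an ANCOVA with factors of treatment and analysis center and the respective Baseline lesion count". The synopsis also refers the reader onward: "All of the testing relating to the analysis of inflammatory and non-inflammatory lesions will use the methods introduced in Section 12".

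**Imputation.** 12.1.7 creates five imputed data sets. For lesion counts, "Each complete data set will be analyzed as specified for the particular analysis". For EGSS it fixes the logistic model as treatment plus analysis center, with no interaction.

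**The concern.** A test that does not reject shows homogeneity only if it would probably have rejected had a center been extreme. This test spreads its information over many degrees of freedom, with few subjects per cell. Followed as written, 12.8.4 would put a statement about center consistency in the study report that the data cannot support. For EGSS the other branch is also in doubt: with sparse cells, whether the exclusion search starts depends on which test statistic the software reports.

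The model-selection rule matters less. It leaves the primary model for two of the three co-primary endpoints dependent on outcome data, for an interval judged against a margin of 2.1 lesions.

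**Working it through.** **1. The plan's own power (12.8.2).** Inputs: 220 per arm; inflammatory reductions 29.9 (SD 11.9) and 26.7 (SD 11.7); non-inflammatory 35.5 (SD 16.3) and 29.9 (SD 16.4).
- Inflammatory: SE = 11.8 × √(2/220) = 1.125; superiority power = Φ(3.2/1.125 − 1.96) = 81.2%.
- Non-inflammatory: SE = 16.35 × √(2/220) = 1.559; Φ(5.6/1.559 − 1.96) = 94.9%.
- Non-inferiority: Φ((3.2 + 2.1)/1.125 − 1.96) = 99.7%, and Φ((5.6 + 2.1)/1.559 − 1.96) = 99.9%.

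The stated powers reproduce. Superiority power is stated for a two-sided t-test, so no interaction term enters it.

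**2. Number of analysis centers.** 660/40 = 16.5 subjects per site, below the minimum of 18 in 12.8.4 (40 × 18 = 720 > 660), so pooling is needed at the planned numbers. At most 36 centers can reach 18 (660/18 = 36.7). The plan does not fix the number after pooling; 20 to 36 equal centers is assumed here.

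**3. Lesion counts: chance of flagging one extreme center.** Suppose IDP-126 does no better than vehicle in one center, so its mean reduction there is 19.6 instead of 29.9 (δ = 10.3; σ = 11.8). With K equal centers and n = 660/(3K) per cell, the interaction F test has 2(K − 1) and 660 − 3K − 1 degrees of freedom, and noncentrality λ = n δ² (1 − 1/3)(1 − 1/K)/σ².

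| K | n per cell | λ | df | Chance that p < 0.10 |
|---|---|---|---|---|
| 20 | 11 | 5.31 | 38, 599 | 24% |
| 36 | 6.1 | 3.02 | 70, 551 | 15% |

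Simulation agrees: 21-23% with unequal sites pooled by the plan's rule (median 17-20 centers) and 15% with 36 centers. Even with no extreme center the test rejects in 10% of trials. For a 10-lesion shift in one large center (67 of 660 subjects, in an assumed layout of 20 unequal centers), detection rises only to 40%.

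**4. EGSS: sparse cells.** Vehicle success is 8.1% (12.8.2). The chance of no vehicle success in a center is 0.919^11 = 39% with 20 centers, or 0.919^6.11 = 60% with 36. The expected number of such centers is 20 × 0.395 = 7.9, or 36 × 0.597 = 21.5. Simulated size of the nominal 10% interaction test with no true interaction (15 to 36 centers; center log-odds SD 0.4 assumed):

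| Statistic | True size |
|---|---|
| Wald | 0% |
| Likelihood-ratio | about 18-32% |
| Pearson chi-square | about 10-22% |

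The Wald test flagged a center with 8.1% IDP-126 success instead of 52.5% in only 0-1% of trials.

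**5. Model selection for lesion counts.** With no true interaction:
- One-sided type I error at the 2.1 margin was 2.4-2.8% for both the additive model and the plan's rule. With five imputations and the pretest run in each, it was 1.9-2.7% for both.
- In the layout of 20 unequal centers (18 to 67 subjects), with equal weight per center assumed when the term is kept, the inflammatory interval widened from 4.43 to 4.86 lesions (4.86/4.43 = 1.10).
- In that layout, at a true difference of zero, the two models disagreed on non-inferiority in 14.5% (inflammatory) and 11.1% (non-inflammatory) of trials. The rule keeps the term in about 10%, so about 0.10 × 14.5% = 1.5% and 0.10 × 11.1% = 1.1% of verdicts change. The simulation with imputation gave 1.7-2.2% for very unequal sites (coefficient of variation 1.2) and 0.1-0.7% otherwise.
- The five imputed data sets disagreed on the pretest in 11-19% of trials.

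**The case against.** **One center may not matter.** The rule speaks of impact on pooled conclusions. One such center among 20 moves the IDP-126 inflammatory mean by 10.3/20 = 0.5 lesion, and against IDP-126. That is fair for a center of average size. But the plan draws its statement from the p-value, not from the size of the shift. With 67 of 660 subjects the same shift is 10.3 × 67/660 = 1.05 lesions, half the margin, and a center can also err in IDP-126's favor.

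**The exclusion branch is harmless.** A reader might infer that whole centers could leave the primary analysis by chance. The documents do not support that: 12.8.4 makes the exclusion a sensitivity analysis and cautions about it, and 12.1.7 keeps the primary EGSS model additive. This objection stands in full.

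**The pretest is mechanical and pre-specified.** A reader might infer that it inflates type I error. It does not. Higher rates appear when true center effects vary, but under either model, so the pretest is not their cause. The synopsis may simply be abbreviating, since it defers to Section 12. What remains is a wording mismatch and a small loss of precision. On imputation, a literal reading lets each data set choose its own model; this is workable, but results from different models could then be combined.

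**Other safeguards.** 12.8.4 also has a treatment-by-site analysis before pooling, but its cells are smaller still. Section 12 defers detail to a separate SAP that is not among the documents. It may name the EGSS statistic; the protocol sentence would still need correcting.

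**Conclusion.** The main point holds. As written, 12.8.4 infers absence of extreme centers from a lesion-count test that misses one clearly extreme center of average size about 76-85% of the time, and from an EGSS test of unstated form whose size ranges from 0% to about 32%. The lesion-count figures rest on 12.8.2 inputs and assumed equal centers. The EGSS figures also rest on assumed site sizes and center variation.

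Model selection is a minor point: no type I inflation, about 1-2% of non-inferiority verdicts changed at zero difference when centers are very unequal, and close to none when they are similar. It should be argued on consistency and precision. It concerns lesion counts only.

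**What to change.** 1. In 12.8.4, delete the sentence that draws a conclusion from p > 0.10. Report the interaction test and the center-exclusion analysis as descriptive only, and display center-specific treatment estimates for all three co-primary endpoints.
2. In 12.1.3 and 12.1.4, delete the include-or-remove sentence. State that the primary model contains treatment, analysis center and the respective Baseline count in every imputed data set, as in the synopsis. In 12.8.4, state that the interaction is fitted separately and never changes the primary model.
3. Clerical: 12.1.3 and 12.1.4 cite Section 12.1.9 for imputation; the text is in 12.1.7.

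Cost: wording and a few lines of code before unblinding. Sample size stays at 220 per arm, and the stated power is unaffected because it never included the interaction. The downside is that a real interaction will appear only in the descriptive check. If the separate SAP already settles these points, only the protocol text needs aligning.
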